4.1.4 Stopping Rules Criteria

The dose-escalation will be halted if, for each route of administration or schedule, either:

- The MTD has been reached as determined by the model ([Appendix 8](#)) and at least 6 participants have been already dosed at the current estimate of the MTD ($\pm 20\%$).
- The maximum of 60 DLT-evaluable participants is reached.

Due to the exploratory nature of this clinical study, any part of its conduct can be discontinued at any time at the discretion of the Sponsor. This will not constitute a

premature termination of the study. The Sponsor will notify the Investigators and Health Authorities if the study is discontinued or the development program is terminated.

4.1.5 Communication Strategy

The Investigators and the Sponsor will communicate regularly and on an ad-hoc basis to discuss the occurrence of any safety events including DLTs. At the end of each treatment cohort, the Sponsor will convene a joint teleconference with the participating Investigators. Dose-escalation decisions and selection of the dose for the next cohort of participants will be guided by the pre-defined escalation steps for Part I and mCRM-EWOC recommendation for Part II in addition to the review of all relevant available data including DLT information. Study Investigators and the Sponsor should reach a consensus on the next dose-level and may include de-escalation and/or expansion of recruitment into particular cohorts.

In addition to these communications, the Sponsor and Investigators will be in regular contact throughout the study by email/telephone per normal interactions during the conduct of a clinical study and, when required the Sponsor will arrange teleconferences and meetings to discuss the study status.

4.2 SCIENTIFIC RATIONALE FOR STUDY DESIGN

The study rationale is provided in Section [2.1](#).

The biomarker/PD assessments in this study are guided by the mode-of-action (MoA) and will focus on measuring CEA-expression (soluble in blood, and tumor by IHC) and immune cell activation in both tumor and blood (soluble and cellular assessments).

4.2.1 Rationale for Modified Continuous Reassessment Method of Escalation with Overdose Control

The Part II dose-escalation of this trial will use a Bayesian model-based approach, i.e., the mCRM-EWOC design ([Neuenschwander et al 2008](#)). The use of Bayesian model-based Phase I designs has been advocated by Rogatko ([Rogatko et al 2007](#)) and is one of the key elements of the Food and Drug Administration (FDA)'s Critical Path Initiative. Clinical judgment can always override the Bayesian adaptive design recommendations in the dose-selection process.

The primary objective of a dose-escalation trial, including the present trial, is to determine a MTD or recommended dose for Phase II. DLTs are the driver of dose-allocation and act as an important factor to define the MTD; however, DLTs are not equal to severe DLTs. DLTs traditionally are defined by the occurrence of severe toxicities during a relatively shorter period of time of systemic cancer therapy, which is called the DLT observation window.

The DLT observation window is usually the first treatment cycle of systemic cancer therapy in order for treated participants to have complete information on toxicities (DLTs)

prior to the next dose assignment in conventional dose-escalation designs. Toxicity induced by *cibisatamab* occurred predominantly within the first few days after the initial administration of the drug. Therefore, in line with this, a 3-week DLT window will be implemented in Part II of this study (or 6-week DLT window if a fractionated dosing schedule is implemented).

The mCRM-EWOC design has many favorable characteristics; first, it adaptively fits a DLT dose-response curve by incorporating toxicity data from eligible participants among different cohorts, and non-clinical or clinical information from compounds with similar MoA contributes by building an informative prior distribution of the statistical model. Second, it locates the MTD efficiently without pre-specifying dose-levels in each cohort. Dose-selections are made based on the DLT dose-response curve measured by a two-parameter logistic model over the dose-range, subject to clinical judgment and mandated safety constraints that limit the size of dose-increments. Moreover, the EWOC algorithm highly reduces risks of exposing participants to overly toxic doses.

Such model-based designs have been successfully applied in many Phase I dose-escalation studies ([Schöffski et al 2004](#); [Le Tourneau et al 2009](#); [Neuenschwander et al 2008](#)).

In addition, hypothetical dose-escalation runs using the design and simulations demonstrate the validity of the operating parameters of the design as implemented for this study ([Appendix 8](#)).

4.2.2 Rationale for Study Population

The study will be conducted in adult male and female participants with locally advanced and/or metastatic CEA-positive solid tumors who have progressed on SOC treatment, are intolerant to SOC, and/or are non-amenable to SOC.

Clinical and non-clinical studies have suggested that a wide array of tumors may respond to CEA-targeted TCBs. Therefore, this study will recruit participants with all types of advanced and/or metastatic solid tumors with cytoplasmic and/or membranous CEA expression in $\geq 20\%$ of cells at intensities greater than at least IHC 1+ on archival material (or fresh biopsy when archival is not available) which are not amenable to SOC treatment. In the single participant cohort part of the study (Part I), participants require a high CEA expression ($\geq 20\%$ of cells at intensity 2+/3+) to ensure interpretability of safety parameters including potential tumor inflammation.

RO7172508 has the potential to bind to circulating sCEA, therefore, the exposure may be impacted following administration of low doses of RO7172508. A maximum baseline sCEA level has been indicated for doses < 12 mg to minimize the impact of RO7172508 binding to sCEA. *Preliminary PK data from the current study suggest sCEA may also impact the clearance of RO7172508. In order to further explore this relationship, at least 3 patients in each cohort in Part II should have a baseline sCEA level of ≤ 20 ng/mL.*

The maximum concentration of sCEA in a participant was calculated in order to observe at least 80% recovery of free RO7172508 at the predicted C_{max} . Assuming instantaneous equilibrium and a monovalent binding of RO7172508 to sCEA, one could express free-concentration of RO7172508 in plasma at time of administration as follows:

$$RO7172508_{free} = \frac{L_{tot} - R_{tot} - K_d - \Delta^{0.5}}{2}$$

$$\Delta = (L_{tot} + R_{tot} + K_d)^2 + 4 \times L_{tot} \times K_d$$

where L_{tot} is the total concentration of RO7172508, R_{tot} is the total concentration of sCEA, and K_d is the dissociation constant of the complex RO7172508-sCEA.

[figure not shown]
All calculations are performed assuming following parameter values:

- $K_d = 390 \text{ pM}$,
- $MW_{RO7172508} = 195000 \text{ Da}$,
- $MW_{sCEA} = 180000\text{-}200000 \text{ Da}$,
- $V_c = 40 \text{ mL.Kg}^{-1}$
- $BW_{human} = 70 \text{ Kg}$

where MW stands for molecular weight, V_c stands for central volume of distribution and BW stands for body weight.

The recovery of RO7172508 at C_{max} was calculated using the above parameters for predicted doses < 12 mg (Figure 6).

Figure 6 Recovery of RO7172508 in the Presence of sCEA

According to those simulations, sCEA concentration expected to produce 80% recovery for RO7172508 at C_{max} for the different clinical doses are presented in [Table 10](#):

Table 10 sCEA Concentrations Predicted to Result in 80% Recovery of RO7172508 at Doses Less Than 12 mg

Dose (μg)	65	160	400	800	1600
sCEA concentration (ng/mL)	22-24	28-31	44-49	70-78	123-137
Dose (mg)	3.2	6.4	12	-	-
sCEA concentration (ng/mL)	229-254	440-489	809-899	-	-

4.2.3 Rationale for Control Group

Not applicable.

4.2.4 Rationale for Biomarker Assessments

RO7172508 was designed to target tumors that express CEA and to concomitantly engage immune cells leading to their activation and proliferation, which culminates in tumor lysis. Non-clinical studies have confirmed the expected MoA of RO7172508 by mediating tumor killing, induction of T-cell activation markers (CD25 and CD69), cytokine release (interferon (IFN) γ , tumor necrosis factor (TNF) α , granzyme B, interleukin (IL)-2, IL-6, and IL-10), and proliferation of T-cells. Furthermore, the MoA of RO7172508 occurs only if simultaneous binding (cross-linking) of T-cells to CEA-expressing tumor cells takes place. RO7172508 treatment may result in changes in peripheral blood immune cells and soluble circulating markers such as cytokines or tumor markers that are related to the MoA of RO7172508. Hence, plasma samples will be collected and analyzed for exploration of soluble factor changes (including but not limited to sCD25, IL-6, IFN γ , TNF α , etc) and tumor markers (including but not limited to sCEA, etc) that may be associated with treatment benefits or toxicities. Blood samples will also be collected and analyzed with respect to alterations in the number and activation/differentiation of immune cells (including but not limited to CD8+/HLA-DR/Ki67+, etc) as a consequence to treatment with RO7172508.

Tumor biopsy samples will only be collected from participants enrolled in Part II of the study. Mandatory tumor biopsies will be performed on two occasions: once during screening (pre-treatment) and once during treatment with RO7172508 on Cycle 2 Day 8), except for NSCLC patients where there is no accessible lesion. An optional biopsy may be taken at disease progression or long-lasting stable disease if the participant consents to this sample being taken. If preliminary data suggest that modification of the on-treatment tumor biopsy time-point would be more appropriate, alternative on-treatment tumor biopsy time-points may be considered in the future cohorts. The goals of these analyses will be (i) to establish a dose–response relationship and (ii) to understand the MoA of RO7172508 at the tumor site.

It is expected that upon treatment, the number and activation/differentiation status of intra-tumoral immune cells as well as their location will change. Such changes will be determined by flow cytometric and/or IHC methods and will be analyzed. Changes such as the density of different immune cell lineages (including but not limited to CD4+ T-cells, CD8+ T-cells, B-cells, natural killer (NK) cells, and macrophages) and their activation/differentiation status (including but not limited to CD25, Ki67, PD1, TIM3, etc) as well as TCR V β repertoire changes will be examined. The expression of tumor markers (including but not limited to PD-L1) will also be examined.

Administration of therapeutic antibodies can be associated with IRRs and cytokine release syndrome (CRS). Therefore, cytokines, including but not limited to IL-6, IFN γ , TNF α , and inflammation markers, will be assessed in serum or plasma samples during treatment and in the event of an IRR/CRS. Because these measurements also represent safety measures, they will be examined in participants enrolled in both Part I and Part II.

The specimens will be used for research purposes to identify biomarkers that are useful to predict and monitor response to RO7172508 treatment and safety, assess PD effects of RO7172508 treatment, and investigate the mechanism of resistance to therapy.

4.3 DOSE JUSTIFICATION

4.3.1 RO7172508

The entry-into-human starting flat dose of 65 μ g was derived from incorporating an integrated approach, which was informed by in vitro activity in high-CEA expressing tumor cells as well as clinical safety experience with *cibisatamab* (see [RO7172508 Investigator's Brochure](#)). Compared to a classical minimum anticipated biological effect level (MABEL) approach, the approach used here reduces the number of participants exposed to sub-therapeutic doses of RO7172508 while ensuring that the starting-dose is in a safe range.

Taking into account 20-fold potency increase, a 400 μ g dose of RO7172508 would be equivalent to 8 mg dose of *cibisatamab* (dose with no relevant cytokine increase documented and no Grade 3-related AEs reported).

Based on the available data, the Sponsor has defined the following intermediate doses in Part I:

- Second cohort: 160 μ g
- Third cohort: 400 μ g
- Fourth cohort: 800 μ g
- Fifth and last cohort: 1.6 mg

Incremental dose-increases may be altered based on emerging PK, PD and safety data but will not exceed 3-fold. If there is no safety concern reported in Part I during the safety

observation period (stopping rule: any RO7172508-related event of Grade ≥ 2 toxicity reported within the DLT window), Part II of the study will start with a dose of 1.6 mg. Dose-escalation for Part II will follow the mCRM-EWOC design (see Section 4.1.2).

A maximum dose of 400 mg Q3W of RO7172508 has been defined. The C_{\max} observed at Cycle 1 of 400 mg (MTD) *cibisatamab* was 113 $\mu\text{g/mL}$. Assuming a potency factor of 20, an equivalent RO7172508 C_{\max} of 5.6 $\mu\text{g/mL}$ is estimated to be achieved by 25 mg. The clinical potency may differ from the in vitro levels; therefore, a maximum dose of 400 mg has been defined to allow this to be tested. The dose-escalation will only take place once a full evaluation of safety data has taken place and the dose-increment levels may be reduced to ensure the participant's safety. Dose-fractionation may also be implemented in Cycle 1 where a dose not exceeding 400 mg will be administered over one cycle e.g., 40 mg on Day 1, 120 mg on Day 8 and 240 mg on Day 15. The maximum SC dose administered QW will be 160 mg QW which is 480 mg over a three-week period/cycle. By applying a conservative bioavailability of $\sim 80\%$ this would equate to 400 mg Q3W IV.

Further details are provided in the [RO7172508 Investigator's Brochure](#).

4.3.2 Obinutuzumab

If required, during the course of this study, based on the incidence of ADA-induced loss of exposure or safety events, obinutuzumab will be administered as detailed in the SoA (Section 1.3). Obinutuzumab will be administered as pre-treatment for RO7172508 either as 2000 mg of obinutuzumab IV on one day (Day -7) or as 1000 mg of obinutuzumab IV on 2 consecutive days (Day -7 and Day -6) as specified in the SoA as per the site's choice. Details regarding the infusion process are provided in Section 6.1. ADA titers and PK of both RO7172508 and obinutuzumab will be monitored as described in Section 4.1.3.

The interval between obinutuzumab and the start of treatment has been determined based on Study BP39365, which is exploring the clinical activity of RO6874281 (FAP-IL2v) in combination with atezolizumab. Five patients were pretreated with obinutuzumab 7 days prior to the combination treatment. It could be confirmed that complete B cell depletion was observed at the start of the combination treatment seven days after obinutuzumab was administered. There was no evidence of ADA formation in these participants when assessing ADA titers for RO6874281 (FAP-IL2v) and atezolizumab (RO5541267) up to 32 weeks of treatment. One patient showed positive ADA titers after 32 weeks of RO6874281/atezolizumab combination, which correlated with the reconstitution of B cells. Another patient remains on study after 52 weeks with no evidence of ADA titers and B cells remain depleted. Without obinutuzumab pretreatment in Study BP39365, the incidence of ADAs is approximately 80%. The kinetics of B-cell depletion and repletion have also been studied in Study BO20999 and following the administration of obinutuzumab a rapid depletion of B-cells was observed by Study Day 8 in CLL patients (first measurement after administration).

Further details are provided in the obinutuzumab Investigator's Brochure.

4.4 END OF STUDY DEFINITION

The end of the study is defined as the date of the last visit of the last participant in the study globally. Because of the exploratory nature of this clinical study, its conduct can be discontinued at any time at the discretion of the Sponsor.

5. STUDY POPULATION

The study population rationale is provided in Section [4.2.2](#).

Participants in this study are patients who have locally advanced and/or metastatic tumors with cytoplasmic and/or membranous CEA expression in $\geq 20\%$ of cells at intensities greater than at least IHC 1+.

In Part I, approximately 5 participants will be enrolled. In Part II, *up to* approximately 75 participants during each dose-escalation, *including additional 15 participants* (150 participants total in both IV and SC) will be enrolled (Section [9.2](#)). *In case the OBD is evaluated with and without obinutuzumab, an additional 15 participants may be enrolled.*

Further participants may be treated in disease-specific expansions, once optimal schedule, route of administration and OBD have been determined.

Prospective approval of protocol deviations from recruitment and enrollment criteria, also known as protocol waivers or exemptions, is not permitted.

5.1 INCLUSION CRITERIA

Participants are eligible to be included in the study only if all of the following criteria apply:

Informed Consent

1. Signed written informed consent and ability to comply with the study protocol according to International Council for Harmonisation of Technical Requirements for Pharmaceuticals for Human Use (ICH) and local regulations.

Age

2. Age ≥ 18 years.

Type of Participants and Disease Characteristics

3. **For Part I** (single participant cohorts), participants with locally advanced and/or metastatic solid tumor with confirmed cytoplasmic and/or membranous high CEA expression in tumor tissue ($\geq 20\%$ of tumor cells staining with CEA IHC 2+ or 3+

intensity) is required (participants without archived tumor tissue available for testing must have a lesion amenable to biopsy). Participants must have progressed on a SOC therapy, be intolerant to SOC, and/or are non-amenable to SOC.

4. For < 12 mg dose cohorts, serum CEA (sCEA) levels below a certain threshold is required as follows:
 - For dose cohorts 65-159 µg, an sCEA level of < 22 ng/mL.
 - For dose cohorts 160-399 µg, an sCEA level of < 28 ng/mL.
 - For dose cohorts 400-799 µg, an sCEA level of < 44 ng/mL.
 - For dose cohorts 800-1599 µg, an sCEA level of < 70 ng/mL.
 - For the dose cohort of 1.6 - 3.1 mg, an sCEA level of < 123 ng/mL.
 - For the dose cohort of 3.2 - 6.3 mg, an sCEA level of < 229 ng/mL.
 - For the dose cohort of 6.4 -11.9 mg, an sCEA level of < 440 ng/mL.

If dose fractionation is implemented, the sCEA threshold for inclusion should correspond to the dose range of the first dose administered.

For Part II, at least 3 participants in each cohort should have a baseline sCEA level \leq 20 ng/mL.

5. For Part II, participants with locally advanced and/or metastatic solid tumor expressing cytoplasmic and/or membranous high-CEA or low-CEA on archival material (or fresh biopsy when archival is not available), who have progressed on a SOC therapy, are intolerant to SOC, and/or are non-amenable to SOC. Participants must have a lesion amenable to biopsy (except participants with NSCLC, which may be enrolled with archival tissue available only). *For participants with colorectal cancer (CRC) only, the CEA assessment by IHC should be performed but the result is not required to enroll the participant.*
 - High-CEA: \geq 20% of tumor cells with IHC 2+ and/or 3+
 - Low-CEA: \geq 20% of tumor cells with the sum of any IHC intensity (1+, 2+ and 3+) and not considered CEA-High
6. Radiologically measurable disease according to RECIST v1.1.
7. Life expectancy (in the opinion of the Investigator) of \geq 12 weeks.
8. Eastern Cooperative Oncology Group (ECOG) Performance Status (PS) 0-1.
9. All acute toxic effects of any prior radiotherapy, chemotherapy, or surgical procedure must have resolved to Grade \leq 1 or returned to baseline except alopecia (any grade) and Grade 2 peripheral neuropathy.
10. Adequate hematological function: neutrophil count of \geq 1.5×10^9 cells/L, platelet count of \geq 100,000/ μ L, and hemoglobin \geq 8 g/dL (4.9 mmol/L) including lymphocytes within normal limits (\geq 0.8×10^9 cells/L).
11. Adequate liver function: total bilirubin \leq $1.5 \times$ the upper limit of normal (ULN; excluding Gilbert's Syndrome), aspartate aminotransferase (AST) and/or alanine aminotransferase (ALT) \leq $2.5 \times$ ULN (in case of liver metastases, \leq $5 \times$ ULN).

12. Adequate renal function: creatinine clearance by Cockcroft Gault formula ≥ 60 mL/min for participants with, in the Investigator's judgment, serum creatinine levels that do not adequately reflect renal function.
13. Adequate lung function: vital capacity and forced expiratory volume in first second $> 65\%$ of age and body-weight predicted normal. Diffusion capacity $> 55\%$ of predicted normal.

Sex

14. Male and female participants

The contraception and abstinence requirements are intended to prevent exposure of an embryo to the study treatment. The reliability of sexual abstinence for male and/or female enrollment eligibility needs to be evaluated in relation to the duration of the clinical study and the preferred and usual lifestyle of the participant. Periodic abstinence (e.g., calendar, ovulation, symptothermal, or post-ovulation methods) and withdrawal are not acceptable methods of contraception.

a) Female Participants

A female participant is eligible to participate if she is not pregnant (see [Appendix 5](#)), not breastfeeding, and at least one of the following conditions applies:

- Women of non-childbearing potential (WONCBP), as defined in [Appendix 5](#).
- Women of childbearing potential (WOCBP), who:
 - Agree to remain abstinent (refrain from heterosexual intercourse) or use contraceptive methods that result in a failure rate of $< 1\%$ per year from screening until 2 months after the last dose of RO7172508. Examples of contraceptive methods with a failure rate of $< 1\%$ per year include bilateral tubal occlusion, male sterilization, and copper intrauterine devices (see [Appendix 5](#)).
 - Have a negative pregnancy test (blood) within one week prior to the first study treatment administration (applicable to premenopausal women and women ≤ 2 years after start of menopause (menopause is defined as amenorrhea for > 2 years)).

b) Male Participants

During the treatment period and for at least 2 months after the last dose of study treatment, agreement to:

- Remain abstinent (refrain from heterosexual intercourse) or use contraceptive measures such as a condom *or a* contraceptive method that result in a failure rate of $< 1\%$ per year, with partners who are WOCBP (as defined in [Section 1](#) of [Appendix 5](#)).
- Refrain from donating sperm during the study.

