 - For the dose cohort of 6.4 -11.9 mg, an sCEA level of < 440 ng/mL.

If dose fractionation is implemented, the sCEA threshold for inclusion should correspond to the dose range of the first dose administered.

For Part II at least 3 participants in each cohort should have a baseline sCEA level ≤20 ng/ml.

5. **For Part II**, participants with locally advanced and/or metastatic solid tumor expressing cytoplasmic and/or membranous on ≥ 20% of tumor cells of high-CEA or low-CEA on archival material (or fresh biopsy when archival is not available), who have progressed on a SOC therapy, are intolerant to SOC, and/or are non-amenable to SOC. Participants must have a lesion amenable to biopsy (except participants with NSCLC, which may be enrolled with archival tissue available only). *For patients with colorectal cancer (CRC) only, the CEA assessment by IHC should be performed but the result is not required to enroll the patient.*
- High-CEA: ≥20% of tumor cells with IHC 2+ and/or 3+
 - Low-CEA: ≥20% of tumor cells with the sum of any IHC intensity (1+, 2+ and 3+) and not considered CEA-High
6. Radiologically measurable disease according to RECIST v1.1.
7. Life expectancy (in the opinion of the Investigator) of ≥ 12 weeks.
8. Eastern Cooperative Oncology Group (ECOG) Performance Status (PS) 0-1.
9. All acute toxic effects of any prior radiotherapy, chemotherapy, or surgical procedure must have resolved to Grade ≤ 1 or returned to baseline, except alopecia (any grade) and Grade 2 peripheral neuropathy.
10. Adequate hematological function: neutrophil count of ≥ 1.5 × 10⁹ cells/L, platelet count of ≥ 100,000/µL, and hemoglobin ≥ 8 g/dL (4.9 mmol/L) including lymphocytes within normal limits (≥ 0.8 × 10⁹ cells/L).
11. Adequate liver function: total bilirubin ≤ 1.5 × the upper limit of normal (ULN; excluding Gilbert's Syndrome), aspartate aminotransferase (AST) and/or alanine aminotransferase (ALT) ≤ 2.5 × ULN (in case of liver metastases, ≤ 5 × ULN).
12. Adequate renal function: creatinine clearance by Cockcroft Gault formula ≥ 60 mL/min for participants with, in the Investigator's judgment, serum creatinine levels that do not adequately reflect renal function.
13. Adequate lung function: vital capacity and forced expiratory volume in first second > 65% of age and body-weight predicted normal. Diffusion capacity > 55% of predicted normal.

Sex

14. Male and female participants

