Symptoms of IRRs and CRS, during or after infusion of RO7172508, may be indistinguishable from each other and might be life-threatening. CRS is a disorder characterized by nausea, headache, tachycardia, hypotension, rash, dyspnea, and renal, coagulation, hepatic and neurologic disorders; CRS is caused by the release of cytokines from cells (Lee et al 2014). Severe CRS may be associated with other clinical sequelae such as disseminated intravascular coagulation and capillary leak syndrome. Standard of care for severe or life threatening CRS resulting from immune-based therapy has not been established, especially in solid tumors.

In case of IRR/CRS, the recommended management is detailed in [Table 17](#).

The activity of RO7172508 at the tumor site leads to the destruction of the tumor cells and tumor inflammation/flare. Given this mechanism of action, AEs associated with tumor inflammation are expected. These AEs are expected to occur shortly following RO7172508 administration and can affect organ systems with the location of the tumor lesions. These events might be life-threatening especially in case of critical location of the tumor (respiratory tract) or extensive tumor size.

Because of a higher affinity to CEA of RO7172508 compared to *cibisatamab*, the severity of adverse reactions may be higher; however, the difference in the potency has been taken into account in the evaluation of the starting-dose proposed in this study. Stringent risk mitigation measures, including required appropriate organ function at baseline (cardiac, pulmonary, liver, hematologic function), close monitoring of participants, especially around the first infusion (including 24-hour hospitalization after the first infusion), staggered enrollment, dose-escalation rules and detailed instructions regarding management of specific AEs are designed to minimize risks. Overall, these potential risks are considered manageable and acceptable in the context of anticipated benefit.

Risk mitigation has been considered in the study design and management of potential AEs is described in *Section 8.3.8 of the protocol* and the [RO7172508 Investigator's Brochure](#).

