5.2 EXCLUSION CRITERIA

Participants are excluded from the study if any of the following criteria apply:

Medical Conditions

1. Participants with a history or clinical evidence of central nervous system (CNS) primary tumors or metastases including leptomeningeal metastases unless they have been previously treated, are asymptomatic, and have had no requirement for steroids or enzyme-inducing anticonvulsants in the last 14 days before screening.
2. Participants with non-irradiated lesions > 2 cm at critical sites (e.g., paraspinal, paratracheal) where tumor swelling induced by RO7172508 is expected to lead to significant complications.
3. Participants with another invasive malignancy in the last 2 years (with the exception of basal cell carcinoma and tumors deemed by the Investigator to be of low likelihood for recurrence).
4. Evidence of significant, uncontrolled concomitant diseases that could affect compliance with the protocol or interpretation of results or contraindicate the use of an investigational drug, including diabetes mellitus and history of relevant pulmonary disorders.

Diagnostic Assessments

5. Uncontrolled hypertension (systolic blood pressure [SBP] > 150 mmHg and/or diastolic BP [DBP] > 100 mmHg), unstable angina, congestive heart failure (New York Heart Association (NYHA) > 1, serious cardiac arrhythmia that requires treatment with the exceptions of atrial fibrillation and paroxysmal supraventricular tachycardia, and history of myocardial infarction within 6 months of enrollment.
6. Active or uncontrolled infections.
7. Known hepatitis B or C (active replicating).
8. Major surgery or significant traumatic injury < 28 days prior to the first RO7172508 administration (excluding biopsies) or anticipation of the need for major surgery during study treatment.
9. Dementia or altered mental status that would prohibit informed consent.
10. Baseline corrected QT interval of > 470 ms. Participants with baseline resting bradycardia < 45 beats per minute (bpm) or baseline resting tachycardia > 100 bpm.
11. Radiotherapy within the last 28 days prior to the first RO7172508 administration with the exception of limited-field palliative radiotherapy.
12. Presence of bilateral lung lesions with either > 3 lesions per lung or ≥ 1 lesion per lung with a diameter > 3 cm (*only unequivocal lesions of > 1cm are to be counted for this criterion, unless there is miliary metastatic-type diffuse disease, then these participants are ineligible*).

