8.3.8.3 Management of Diarrhea/Colitis

[Table 19](#) provides guidelines for management of suspected diarrhea.

Patients should be closely monitored (including monitoring of renal function) and should be hydrated if clinically indicated to prevent renal insufficiency due to fluid depletion.

For Grade ≥ 2 diarrhea associated with the 3rd administration of RO7172508 or later, patient referral to a GI Specialist is recommended (including a colonoscopy and/or biopsy based on specialist input).

Table 19 Management of Diarrhea/Colitis

Event	Management Recommendations
Grade 1	
 • Continue treatment with RO7172508. • Initiate anti-diarrheal treatment (e.g., loperamide) as soon as possible. • Monitor the participant closely. • Ensure appropriate fluid intake. • If symptoms persist despite optimal anti-diarrheal treatment for more than 5 days, perform gastrointestinal (GI) work up*.
Grade 2	
 • Withhold treatment with RO7172508. • Initiate anti-diarrheal treatment (e.g., loperamide) as soon as possible • Monitor the participant closely, perform GI work up*. • Ensure appropriate fluid intake • If symptoms do not improve to Grade ≤ 1 despite optimal anti-diarrheal treatment within 2 days, consider treatment with IV or oral corticosteroids (1mg/kg/day oral prednisolone or equivalent). • If diarrhea does not improve after 48 hours of corticosteroid treatment of 1mg/kg/day, increase dose to 2mg/kg/day. • If symptoms do not resolve despite corticosteroid treatment, consider referring the participant to GI specialist • RO7172508 can be re-started if symptoms resolve to Grade ≤ 1.
Grade 3	
 a. Withhold treatment with RO7172508. b. Refer the participant to GI specialist for diagnostic procedures (stool culture, endoscopy) and appropriate treatment. 
 • Initiate corticosteroid treatment IV (2mg/kg/day IV methylprednisolone or equivalent). • Ensure appropriate fluid intake. • RO7172508 can be re-started if symptoms resolve to Grade ≤ 1. • If no improvement after 24 hours, consider treatment as per Grade 4 guidelines

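### Inclusion criterion 12 gives a numeric renal limit only when serum creatinine is judged unreliable; when creatinine is judged reliable, including when it shows impairment, no numeric limit is stated

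*Combined protocol and SAP*

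**What the plan says.** Criterion 12 in Section 5.1 opens with "Adequate renal function: creatinine clearance by Cockcroft Gault formula", gives a limit of at least 60 mL/min, and then restricts that limit to a subgroup: "for participants with, in the Investigator's judgment, serum creatinine levels that do not adequately reflect renal function". The synopsis (Section 1.1) has the same criterion: "Adequate renal function: creatinine clearance by Cockcroft Gault formula ≥ 60 mL/min for participants with, in the Investigator's judgment, serum creatinine levels", with the same ending. Neither place adds a limit for participants outside the subgroup.

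The neighbouring organ-function criteria are built differently. Criterion 11 begins "Adequate liver function: total bilirubin" and sets limits for everyone, with a separate transaminase limit for liver metastases. Criteria 10 (hematology) and 13 (lung) also carry numeric limits for all participants.

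The exclusion criterion closest to the subject is number 4 in Section 5.2: "Evidence of significant, uncontrolled concomitant diseases that could affect compliance with the protocol or interpretation of results". It also reaches conditions that would contraindicate an investigational drug. It does not name the kidney and gives no renal value.

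Appendix 4 lists creatinine in the clinical chemistry panel without an eligibility cut-off.

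**The concern.** The 60 mL/min test depends on doubt about the creatinine value. Where there is no doubt, the test is not called for. A participant whose creatinine is raised, and is accepted as a true reading, is thus the one for whom the text states no number. Two sites could decide differently on the same laboratory values without either departing from the protocol.

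This matters more here than in many studies. It is a first-in-human T-cell engager without in vivo toxicity studies (Section 2.2.1). Sections 2.3 and 8.3.8.1 count renal disorders among the features of cytokine release syndrome. Section 8.3.8.3 asks for renal monitoring in diarrhea and says that patients "should be hydrated if clinically indicated to prevent renal insufficiency due to fluid depletion". Sections 5 and 8 do not allow waivers, so what the criterion says is what sites have to apply.

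**Working it through.** The plan gives no figure to reproduce. The check is one of wording, with one illustration.

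**Step 1: what criterion 12 states in each case.**

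| Investigator's view of serum creatinine | Numeric renal limit stated |
|---|---|
| Does not reflect renal function | Clearance at least 60 mL/min |
| Reflects renal function, value normal | None |
| Reflects renal function, value raised | None |

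The third row is the gap.

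**Step 2: whether another provision fills it.**
- Inclusion criteria 10, 11 and 13 cover blood, liver and lung, not kidney.
- Exclusion 4 rests on judgement and has no renal threshold. Stable chronic impairment need not count as uncontrolled.
- Creatinine is measured (Appendix 4), and the schedules in Section 1.3 require chemistry results to be reviewed before dosing, but no value is attached to that review.
- Section 2.3 lists the baseline organ function relied on as risk mitigation: "required appropriate organ function at baseline (cardiac, pulmonary, liver, hematologic function". Renal function is not in the list.

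No provision supplies a number for the third row.

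**Step 3: illustration.** The protocol names the Cockcroft-Gault formula without writing it out; the usual form is used here. The participant is assumed: a woman aged 72, weight 60 kg, creatinine 2.5 mg/dL, judged representative.

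- Clearance = (140 − age) × weight / (72 × creatinine) × 0.85 for women
- = (140 − 72) × 60 / (72 × 2.5) × 0.85
- = 4080 / 180 × 0.85
- = 22.67 × 0.85 = 19.3 mL/min

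Against the protocol's own limit: 19.3 / 60 = 0.32, about a third. Because her creatinine is taken as reliable, criterion 12 does not call for that comparison.

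**The case against.** The strongest reply is that criterion 12 starts from a general requirement of adequate renal function. On that reading the clearance test is only a tool for cases where creatinine is uninformative, and a participant with openly impaired function fails the general requirement. Exclusion 4 can be used as well, since it is aimed at disease that would affect interpretation or contraindicate the drug. Chemistry is reviewed before dosing, and participants are assigned to a group and dose in consultation with the sponsor (Section 6.3.1). All of this stands. It means that an Investigator may decline such a candidate. It does not give a threshold, so the decision has no stated number behind it.

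Some stronger readings are tempting, and the documents do not support them:
- **That such a participant automatically qualifies, with no limit of any kind.** The general requirement and exclusion 4 are still there; what is absent is a numeric limit.
- **That a serum-creatinine limit was dropped by mistake.** The clause reads as if it once qualified such a limit, but neither the synopsis nor Section 5.1 shows one, so this is inference.
- **That moderately raised creatinine shows the same gap.** For the same woman at 1.3 mg/dL, clearance is 4080 / 93.6 × 0.85 = 37 mL/min. A modest creatinine beside a much lower clearance may be just the mismatch the clause is meant to catch, and the 60 mL/min limit would then apply.
- **That dose-limiting toxicity counts would be distorted.** Section 4.1.3.1 leaves out events attributable to underlying disease, so a renal event in an impaired participant could be counted or not. The direction is open and no frequency is given.
- **That Section 2.3 relies on baseline renal function.** Its list does not include it.

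Reliance on Investigator judgement is not in itself a fault; inclusion 7 and exclusion 3 use it openly.

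**Conclusion.** The point holds as a gap in a stated rule. Criterion 12 has one numeric renal limit and applies it only when creatinine is doubted. A participant whose creatinine correctly shows impairment is not tested against it, and no other section supplies a limit. In the assumed example a clearance of about 19 mL/min goes unchecked against 60.

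The finding about the wording is firm, because the same sentence stands in two places in the current text. The size of the consequence is not known: the documents give neither the expected distribution of renal function among candidates nor any rate of renal events. The example shows that the gap exists, not how often it would be met. The change should be made, since the cost is small and the study itself expects renal involvement in some of its toxicities.

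**What to change.** Reword criterion 12 identically in Section 5.1 and in the synopsis so that a stated renal requirement binds every participant. There are two ways to do this:

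1. Remove the qualifying clause, so that the limit already printed applies to all.
2. Keep the clause for doubtful creatinine, and have the sponsor state the serum-creatinine condition that applies when creatinine is considered reliable.

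The sponsor decides which requirement, and which value, is intended.

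The cost is one sentence in two places. No new data are needed: creatinine is in the chemistry panel (Appendix 4), weight is recorded at screening (Section 8.2.1), and age and sex are in the demographic data (Section 8.2.5). The downside is that some candidates with reduced clearance would no longer qualify; the documents do not allow their number to be estimated.
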